Statistical analysis	
Data processing and statistical analysis will be carried out by the service provider, Axonal-Biostatem.
 
The statistical analyses will be described in a Statistical Analysis Plan (SAP) validated by the Sponsor and the Scientific Committee, prior to the freeze-in.
 
Statistical analyses will be performed after baseline freezing of the data with SAS® software (SAS Institute, NC, Cary, USA), version 9.4 or later.
 
Demographic and efficacy/performance analyses will be performed in the ITT population. The primary endpoint will be analyzed in PP (Per Protocol) and then validated in the ITT (intention to treat) population. The safety analyses will be performed in the safety population.
 
For quantitative variables, the usual statistics (n, missing n, mean, standard deviation (SD), median, first and third quartiles (Q1 and Q3), minimum and maximum) will be presented. IC95% may be

	
presented if relevant (especially for the primary endpoint).
 
For categorical variables, the usual statistics (n, missing n, frequency and percentage) for each modality will be provided.
 
Descriptive statistics will be provided in aggregate and by pump group.
 
The type 1 error, α, is set at 5% when the tests used will be two-sided (superiority) and α will be set at 2.5% when the tests will be one-sided in the case of Noninferiority (IC95%).
 
Analysis of the main objective
 
The non-inferiority analysis will be produced via an Ancova or mixed model on the Per-Protocol population and then on an intention-to-treat basis.
 
If non-inferiority is demonstrated, a superiority analysis will be conducted.
 
Analysis of secondary objectives
 
The secondary criteria will be described and then be the subject of mixed or Ancova models.
 
A non-inferiority analysis on HbA1c data and superiority analyses on Time in range, number of glycemic events, patient satisfaction will be performed.

Regulatory framework	ID-RCB number, CPP opinion, CNIL MR001 and RGPD compliance, information to the ANSM, approval of investigator contracts by the CNOM, transparency obligations
Logistics	CRO Axonal-Biostatem (Nanterre, France)

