11.2.4 Analysis of the effectiveness / performance of the device

Analysis of primary efficacy endpoint:

The non-inferiority analysis of the primary efficacy endpoint will be performed with an ANOVA, with the DM as an explanatory variable, on the *per protocol* population and then on the *intention-to-treat* population. If the upper bound of the IC95% of the Omnipod-Medtrum estimated difference in means (LSmeans) exceeds the non-inferiority bound, it will be rejected.

Non-inferiority bounds are defined in this protocol and will be used in the statistical analysis plan.

If non-inferiority is demonstrated, a superiority analysis will be conducted.

Secondary efficacy endpoint analyses:

The secondary efficacy endpoints will be analyzed for the variables listed below.

Each variable will be described globally and by pump group.

In case of non-inferiority analysis, the same methodology as for the primary endpoint will be used.

In case of comparison of quantitative variables, parametric (T-test) or non-parametric (Mann-Whitney) tests of comparison of means will be used. In case of comparison of qualitative variables, CHI² or Fisher exact tests will be used.

In case of tests on changes within each group, paired data tests will be used (paired data T-test or Wilcoxon signed ranks test, depending on the distribution of the data).

❖ **HbA1c:**

- Evolution of the value measured in the laboratory from a blood sample taken before the D0 visit and just before the 3-month visit
- Description in the total population, in each group and comparison between groups.

❖ **Glucose measurements**

- Average of glucose measurements over each period and over the entire study duration
- Description of the minimum and maximum values over the total duration of the study
- Description of the % of Time in Range (see ADA and International Consensus on Time in Range recommendations^{25,26})
- Description in the total population, in each group and comparison between groups.

❖ **Glycemic events**

- Description of the number of symptomatic and non-symptomatic hypoglycemic events during the evaluation period, broken down by severity level (see ADA consensus definitions²⁵)
- Description of the number of symptomatic and non-symptomatic hyperglycemia events during the evaluation period, broken down by severity level (see ADA consensus definitions²⁵)
- Description in the total population, in each group and comparison between groups.
-

❖ **Device tolerance**

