4.4.2 Secondary endpoints

The secondary endpoints were:

- HbA1c:
 - Value measured in the laboratory from a blood sample taken before the D0 visit and just before the 3-month visit
- Glucose Level Measurements
 - Average of glucose measurements over each time period and over the entire study duration
 - Minimum and maximum values
 - Time in range expressed as a %.

These values were automatically calculated by the FreeStyle Libre software and will be reported by the investigator.

- Glycemic events
 - Number of symptomatic and non-symptomatic hypoglycemic events during the evaluation period, broken down by severity level
 - Number of symptomatic and non-symptomatic hyperglycemia events over the evaluation period, broken down by severity level

This information was derived from the Free Freestyle data and the data entered by the patient in the MDP.

The definition of hypoglycemia and hyperglycemia is the ADA consensus definition:

Table 1—Summary of consensus definitions			
Outcome	Definition		
Hypoglycemia	Level 1: glucose <70 mg/dL (3.9 mmol/L) and glucose \geq 54 mg/dL (3.0 mmol/L) Level 2: glucose <54 mg/dL (3.0 mmol/L) Level 3: a severe event characterized by altered mental and/or physical status requiring assistance		
Hyperglycemia	Level 1—elevated glucose: glucose $>$ 180 mg/dL (10 mmol/L) and glucose \leq 250 mg/dL (13.9 mmol/L) Level 2—very elevated glucose: glucose $>$ 250 mg/dL (13.9 mmol/L)		
Time in range	Percentage of readings in the range of 70–180 mg/dL (3.9–10.0 mmol/L) per unit of time		

- Device tolerance
 - Local skin tolerance at the pump site (adhesive hold) and at the FreeStyle Libre blood glucose sensor site (adhesive hold)
 - Any local or systemic safety issues were to be reported during the study, including the additional one-month phase at the end of the study for patients in the Omnipod group
- Incidents with devices
 - Any type of incident involving the operation of the medical devices used, especially for pumps: pulling out, control problems, transmission difficulties, occlusion, leakage, etc.
- Patient satisfaction
 - Self-questionnaire evaluating satisfaction with the use of the device (pump + PDM)

- Final question regarding patient preference between the Medtrum device and the Insulet device
- Insulin treatment
 - The insulin treatment used should be documented

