4.4.3 Calculated/derived criteria

			2 = "More than 10 years
Number of years and months of treatment per pump	PUMP_D = Number of years * 12 + number of months	Time since starting pump therapy (in months)	Digital
Weight (kg) and height (cm)	BMI_D = (weight/height ²)*10000	Body Mass Index (BMI)	Digital
IMC_D	IMC4CL_D = -0 if BMI_D<18.5 -1 if BMI_D = [18,5 ; 25[-2 if BMI_D = [25; 30[. -3 if BMI_D >= 30	BMI (in classes)	0 = "Less than 18.5 1 = " [18,5 ; 25[" 2 = " [25 ; 30[" 3 = "Greater than 30
Tolerance variables	AL_PBTOL_D = -1 if the patient reported during the follow-up an irritation/itching problem or a redness problem or another adverse event -0 otherwise	Patient with at least one tolerance problem	0 = "No 1 = "Yes
HbA1c value measured in the laboratory at D0 and 3M	EVOL_HBA1C_D = HbA1c at M3 - HbA1c at D0	Evolution of HbA1c between D0 and 3M	Digital
Estimated HbA1c (FSL) (%)	EVOL_eHbA1c = HbA1c estimate at V2 - HbA1c estimate at D0 (will also be calculated for V3 and V4)	Evolution of HbA1c estimation between D0 and V2,V3,V4	Digital
Average blood glucose at different follow-up times	EVOL_GLYC_V2 = Average blood glucose at V2 - Average blood glucose at D0 (will also be calculated for V3 and V4)	Evolution of the average blood glucose level between D0 and V2, V3, V4	Digital
Average daily basal dose at different follow-up times	EVOL_BASAL_V2 = Average daily basal dose at V2 - Average daily basal dose at D0 (will also be calculated for V3 and V4)	Evolution of the average daily basal dose between D0 and V2, V3, V4	Digital
Average daily bolus dose at different follow-up times	EVOL_BOLUS_V2 = Average daily bolus dose at V2 - Average daily bolus dose at D0 (will also be calculated for V3 and V4)	Evolution of the average daily bolus dose between D0 and V2, V3, V4	Digital

Number of Boluses/day at different follow-up times	EVOL_NB_BOLUS_V2 = Number of Boluses/day at V2 - Number of Boluses/day at D0 (will also be calculated for V3 and V4)	Evolution of the number of Bolus/day between D0 and V2, V3,V4	Digital
Time of wearing the FSL	PORT_70sup = -1 wear time greater than 70%. -0 otherwise	FSL wear time greater than 70%.	0 = "No 1 = "Yes

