7.4 ANALYSIS OF THE EVALUATION CRITERIA

7.4.1 Primary endpoint analysis

The primary endpoint is the estimate of HbA1c at 3 months based on the mean of continuous glucose measurements obtained during the last 10 weeks of follow-up.

HbA1c estimation will be described by treatment group and then by type of diabetes.

The non-inferiority analysis of the primary efficacy endpoint will be performed with an ANCOVA, with the medical device as an explanatory variable and an adjustment on the estimate of HbA1c at Baseline, on the PP population.

If the upper bound of the IC95% of the Omnipod-Medtrum estimated difference in means (LSmeans) exceeds the non-inferiority bound set at 0.4, non-inferiority will not be demonstrated.

If non-inferiority is demonstrated, a superiority analysis will be conducted. If the upper bound of the IC95% of the estimated difference in mean is less than -0.3, superiority will be demonstrated.

The MIXED procedure (SAS® 9.4) will be used.

Code:

```
proc mixed data=XX order=data;
where PP = 1;
class DM;
model ESTIM_HBA1c = ESTIM_HBA1c_BASELINE DM;
lsmeans DM / diff=control cl;
run;
```

A sensitivity analysis will be performed on the ITTm population with imputation of missing data by the mean or median according to the distribution of the primary endpoint.

A subgroup analysis will be performed on the population of patients with an LSP wear rate >70% at M3.

Exploratory analysis:

Univariate analyses will be conducted on age in 2 classes (below or above the median), sex, type of diabetes, center, and duration of diabetes in 3 classes (<5 years; between 5 and 10 years; >10 years). If the p-value <0.05, the variable will be included in the full model. Then a top-down stepwise strategy will be conducted to select the variables for the final model.

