7.4.2 Secondary endpoint analyses

Analyses will be performed on the ITTm population.

Each variable will be described globally and by pump group.

The secondary endpoints are:

1. HbA1c

The evolution of HbA1c (measured in the laboratory) between D0 and 3M will be described, and a comparison between the groups will be made using a Student's t test or a Mann and Whitney test.

2. Glucose level measurement

The mean blood glucose level and its standard deviation (Blood Glucose Deviation SD) will be described over each period (between V1 and V2, then between V2 and v3, then between V3 and V4) and over the total duration of the study (mean, median, standard deviation, Q1-Q3, minimum and maximum). The coefficient of variation of glucose values will also be described.

The evolution of the average blood glucose level compared to baseline will be described at each visit.

FSL wear time (%) will be described.

The % of blood glucose values spent in target (time in range: [70; 180]), hypoglycemia (<70mg/dl), and hyperglycemia (>180 mg/dl) will be described over each time period in each pump group and in the total population.

For these criteria, comparisons between groups will be made using the Student or Mann-Whitney test.

3. Glycemic events

The number of hypoglycemic events will be described overall and in each period by severity level (according to ADA consensus definitions) overall and in each pump group.

Comparisons between groups will be made using Student or Mann-Whitney tests.

The % of time spent in hyperglycemia will be described overall and over each period and in each pump group. Comparisons between groups will be made using Student's t test or Mann and Whitney test.

4. Device tolerance

The analysis of this criterion is detailed in section 7.4 of this document.

5. Incidents with devices

The following criteria will be described for each period and by pump group (after reclassification):

- Pump occlusion (yes; no)
 - If yes, number of times
- Pump detachment (yes; no)
 - If yes, number of times
- Complete stop / breakage of the pump (yes; no)
 - If yes, number of times
- Other pump malfunction (yes; no)
 - All other possible malfunctions will be listed.

6. Patient satisfaction

The following criteria will be described for each period and by pump group:

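### Laboratory HbA1c is compared as a raw change score without adjustment for its collected D0 value; ANCOVA would be at least as precise at no cost, by an amount that depends on a correlation the documents do not give

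*SAP*

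**What the plan says.** SAP 4.4.2 lists laboratory HbA1c as a secondary endpoint: "Value measured in the laboratory from a blood sample taken before the D0 visit and just before the 3-month visit". SAP 4.4.3 derives the change as "EVOL_HBA1C_D = HbA1c at M3 - HbA1c at D0". SAP 7.4.2 item 1 describes that change in the ITTm population, "and a comparison between the groups will be made using a Student's t test or a Mann and Whitney test". It names no covariate and requires no estimated difference or confidence interval for this outcome.

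For the sensor-estimated HbA1c, SAP 7.4.1 specifies an ANCOVA "with the medical device as an explanatory variable and an adjustment on the estimate of HbA1c at Baseline".

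The protocol points two ways. Its synopsis (Statistical analysis) says: "The secondary criteria will be described and then be the subject of mixed or Ancova models". Section 11.2.4 instead provides t or Mann-Whitney tests for ordinary comparisons of quantitative variables, and the SAP follows that section.

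**The concern.** A change score fixes the slope of the 3-month value on the D0 value at 1. With similar SDs at the two visits the true slope is about rho, which is below 1. The change score then subtracts too much of the baseline. Its variance is larger than that of ANCOVA, and any chance D0 difference between the arms carries further into the estimate.

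Laboratory HbA1c is the only HbA1c outcome that does not come from the sensor, so it is the natural check on a sensor-derived primary endpoint. A wider interval weakens that check. If the Mann-Whitney test is chosen, there is also no mean difference to set beside the LS-mean difference of the primary analysis.

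**Working it through.** **Inputs from the documents.** Margin 0.4, one-sided alpha 2.5%, power 80%, assumed difference 0; SD 0.55 as first planned and 0.8 at the blinded review, the latter for the sensor estimate; 100 patients included (all SAP 5.1). ITTm removes 4 patients (SAP 7.1.3). That leaves at most 96, or about 48 per arm if the four are evenly split.

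**Assumptions.** Rho between D0 and 3-month laboratory HbA1c is not in the documents and is varied from 0.5 to 0.9. No laboratory SD is given, so 0.8 is borrowed from the sensor estimate and used at both visits. No target difference is set for this endpoint, so 0.4 is borrowed from the primary margin as a yardstick.

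**The plan's own figures.** n per arm = 2(1.96 + 0.8416)² × SD² / 0.4². SD 0.8 gives 62.8, rounded up to 63 per arm and 126 in total. SD 0.55 gives 29.7, rounded up to 30 per arm and 60 in total; 60/0.8 = 75. All match SAP 5.1.

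**Precision.** With equal SDs:

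- change score: SD_c = 0.8 × √(2(1 − rho))
- ANCOVA: SD_a = 0.8 × √(1 − rho²)
- variance ratio ANCOVA / change = (1 + rho)/2
- half-width = 1.96 × SD × √(2/48)
- power: noncentral t, two-sided 5%, difference 0.4

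| rho | SD change / ANCOVA | Variance ratio | Half-width change / ANCOVA | Power change / ANCOVA |
|---|---|---|---|---|
| 0.5 | 0.800 / 0.693 | 0.75 | 0.320 / 0.277 | 68% / 80% |
| 0.7 | 0.620 / 0.571 | 0.85 | 0.248 / 0.229 | 88% / 92% |
| 0.8 | 0.506 / 0.480 | 0.90 | 0.202 / 0.192 | 97% / 98% |
| 0.9 | 0.358 / 0.349 | 0.95 | 0.143 / 0.140 | about 100% / about 100% |

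A simulation with 48 per arm gave variance ratios of 0.74, 0.87 and 0.97 at rho 0.5, 0.7 and 0.9, close to the formula.

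**If the SDs differ.** Take 0.8 at D0 and 0.9 at 3 months (assumed). Then SD_c = √(0.8² + 0.9² − 2 × rho × 0.8 × 0.9) and SD_a = 0.9 × √(1 − rho²). Power is 62% against 70% at rho 0.5, 83% against 86% at 0.7, and 94% against 95% at 0.8. From the unrounded values the gain is about 8 points, about 2 points and under 1 point.

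**Chance imbalance.** The standard error of the D0 difference is 0.8 × √(2/48) = 0.163. With equal SDs, an imbalance of one standard error separates the two estimates by (1 − rho) × 0.163: 0.08 at rho 0.5, 0.05 at 0.7, 0.03 at 0.8 and 0.02 at 0.9.

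**The case against.** The strongest reply is that nothing here is invalid. The change score already uses D0 and is unbiased under randomization, the endpoint is secondary, and both documents say that the secondary objectives are to describe. At rho 0.8 or above the difference hardly matters. The entry range of 6.5% to 9.5% may compress the D0 spread but not the 3-month spread, which would reduce the gain further. All of this stands. It limits the size of the point but gives no reason to prefer the change score.

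A reader might infer more than the documents support:

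- *That the analysis is biased.* It is not. The shift under chance imbalance is conditional on the allocation that happens to arise and averages out over randomization.
- *That the SAP breaks a clear protocol commitment to baseline-adjusted ANCOVA.* The synopsis leans that way, and it also lists "A non-inferiority analysis on HbA1c data and superiority analyses on Time in range". For such analyses section 11.2.4 says: "In case of non-inferiority analysis, the same methodology as for the primary endpoint will be used". In that section, however, the primary method is an ANOVA with device alone and no baseline covariate, and t or Mann-Whitney tests are provided for ordinary comparisons. The protocol is mixed. Whether laboratory HbA1c should be tested for non-inferiority is a separate question; the case for adjustment is the same either way.
- *That the acknowledged power below 80% applies here.* SAP 5.1 makes that statement about the primary endpoint. The SAP sets no power or margin for laboratory HbA1c.
- *That a disagreement between the two HbA1c outcomes could be put down to the method alone.* The primary is analysed in PP and the secondary in ITTm, and a laboratory sample is not a 10-week sensor mean. Aligning the models removes one source of difference and leaves those two.

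**Conclusion.** The point holds as a free gain in precision on a secondary endpoint. It is not an error that threatens the trial's conclusion. With equal SDs the change score has a larger variance than ANCOVA for every rho below 1. In the equal-SD table its interval is wider by about 15% at rho 0.5, 8% at 0.7, 5% at 0.8 and 3% at 0.9. The 12-point power gain at rho 0.5 is the top of the range examined and should not be read as the expected effect; it falls to about 4 points at 0.7, 1 at 0.8 and nothing visible at 0.9. These sizes rest on an assumed rho, a borrowed SD, equal SDs at the two visits and 48 per arm, which is the ITTm maximum before any missing laboratory values. The direction does not depend on them: apart from one degree of freedom, ANCOVA is not expected to be less precise.

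**What to change.** In SAP 7.4.2 item 1, replace the t or Mann-Whitney comparison with an ANCOVA of 3-month laboratory HbA1c, with D0 laboratory HbA1c and device as terms. Report the Medtrum minus Omnipod LS-mean difference with its 95% CI. State that the population is ITTm: the SAP 7.4.1 code can be reused, but its filter to the per-protocol population must be changed and the laboratory variables substituted. Keep EVOL_HBA1C_D as a descriptive variable. The cost is a short SAP edit and a small change to existing code, with no new data.

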11.2 STATISTICAL ANALYSIS

11.2.1 *General statistical methods*

Data processing and statistical analysis will be carried out by the service provider, Axonal-Biostatem.

The statistical analyses will be described in a Statistical Analysis Plan (SAP) validated by the Sponsor and the Scientific Committee, prior to the freeze-in.

Statistical analyses will be performed after baseline freezing of the data with SAS® software (SAS Institute, NC, Cary, USA), version 9.4 or later.

Demographic data analyses will be performed in the ITT. Safety analyses will be performed in the Tolerance population. Non-inferiority analyses will be performed in the Per Protocol population and validated in the ITT population.

For quantitative variables, the usual statistics (n, missing n, mean, standard deviation (SD), median, first and third quartiles (Q1 and Q3), minimum and maximum) will be presented.

IC95% may be presented if relevant (especially for the primary endpoint).

For categorical variables, the usual statistics (n, missing n, frequency and percentage) of each modality will be provided.

Descriptive statistics will be provided in aggregate.

The type 1 error, α , is set at 5% for all analyses.

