6 MODIFICATIONS TO THE ANALYSES PROVIDED FOR IN THE PROTOCOL

Not applicable

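### The SAP omits, without recording it, the non-inferiority analysis of laboratory HbA1c promised in the protocol synopsis and keeps only a difference test that cannot show non-inferiority

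*SAP*

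**What the plan says.** The protocol synopsis, under the analysis of secondary objectives, states: "A non-inferiority analysis on HbA1c data and superiority analyses on Time in range, number of glycemic events, patient satisfaction will be performed". It also says of method: "The secondary criteria will be described and then be the subject of mixed or Ancova models". The primary endpoint has its own paragraph just before this. The only HbA1c measure among the secondary endpoints (synopsis and protocol 10.2) is the laboratory value at D0 and 3 months.

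Protocol 11.2.4 differs. For secondary comparisons it says: "In case of comparison of quantitative variables, parametric (T-test) or non-parametric (Mann-Whitney) tests of comparison of means will be used". It lists laboratory HbA1c for description and between-group comparison, without calling it a non-inferiority endpoint, but the same section provides: "In case of non-inferiority analysis, the same methodology as for the primary endpoint will be used". Protocol 11.2.1 fixes the populations: "Non-inferiority analyses will be performed in the Per Protocol population and validated in the ITT population".

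SAP 7.4.2 opens with "Analyses will be performed on the ITTm population". For the D0 to 3-month change in laboratory HbA1c it says that "a comparison between the groups will be made using a Student's t test or a Mann and Whitney test". It gives no margin and no decision rule. SAP section 6, headed "MODIFICATIONS TO THE ANALYSES PROVIDED FOR IN THE PROTOCOL", is marked not applicable. The table templates in SAP section 8 allow 95% confidence intervals but do not require them.

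**The concern.** The synopsis names the endpoint and the type of analysis, and protocol 11.2.1 and 11.2.4 supply the populations and the method. The SAP carries out none of this and does not say so.

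This is a non-inferiority trial whose primary endpoint is a sensor-derived HbA1c estimate, taken from manufacturer software and not recalculated. Laboratory HbA1c is the only HbA1c measure that does not come from the sensor, so readers will look to it for corroboration. Under the SAP it can neither support nor contradict non-inferiority. A finding of no significant difference could be offered as reassurance although the data are compatible with a difference above 0.4. With a precise measure, the reverse can happen: a difference is declared significant although its upper limit lies below 0.4, and no rule says how to read it. If the Mann-Whitney route is taken, the test yields no mean difference to set against a margin.

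A lesser point is precision. Laboratory HbA1c does use its baseline, through the change score in SAP 4.4.3, so its main loss is the missing decision rule. Time in range has a baseline value (SAP 7.3) but no derived change score, so it is compared on follow-up values alone. For insulin doses, the change from baseline is only described.

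**Working it through.** **The plan's own figures.** Sample size per arm = 2 × (1.960 + 0.842)² × SD² / 0.4².
- SD 0.55: 29.7, so 30 per arm, 60 in total; 60 / 0.8 = 75 randomised.
- SD 0.8: 62.8, so 63 per arm, 126 in total.

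These match protocol 11.1 and SAP 5.1 and are not in dispute. No sample size or power is stated for laboratory HbA1c.

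**Inputs for laboratory HbA1c.**
- SD 0.8 at D0 and 3 months: an assumption, borrowed from the blinded baseline review of the sensor estimate (SAP 5.1).
- 48 per arm: 100 included (SAP 5.1) minus 4 COVID-19 discharges (SAP 7.1.3), assumed to split equally with complete laboratory data.
- Alternative of 40 per arm: 100 × 0.8 / 2, using the plan's 20% non-analysable share.
- Margin 0.4: assumed to carry over from the primary endpoint.
- Correlation r between D0 and 3 months: not in the documents, so varied from 0.5 to 0.9.

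**Formulas.** SD of change = 0.8 × √(2(1 − r)). SE = SD of change × √(2/n). Largest non-significant difference = 1.96 × SE, and its upper 95% limit is twice that. If the true difference is 0.4, P(non-significant) = Φ(1.96 − 0.4/SE) − Φ(−1.96 − 0.4/SE).

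| | r = 0.5 | r = 0.7 | r = 0.8 | r = 0.9 |
|---|---|---|---|---|
| SD of change | 0.800 | 0.620 | 0.506 | 0.358 |
| Largest non-significant difference, n = 48 | 0.320 | 0.248 | 0.202 | 0.143 |
| Its upper 95% limit, n = 48 | 0.640 | 0.496 | 0.405 | 0.286 |
| Its upper 95% limit, n = 40 | 0.701 | 0.543 | 0.443 | 0.314 |
| P(non-significant, true difference 0.4), n = 48 | 31% | 11% | 2.8% | 0.02% |
| P(non-significant, true difference 0.4), n = 40 | 39% | 18% | 5.8% | 0.1% |

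The upper limit equals 0.4 at r = 0.805 with 48 per arm and at r = 0.837 with 40 per arm. Below those values, a non-significant result can be compatible with more than the margin. An interval rule holds the chance of declaring non-inferiority at a true difference of 0.4 to 2.5%, whatever r is.

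At r = 0.9 and 48 per arm, observed differences from 0.143 to 0.4 − 0.143 = 0.257 would be significant and still meet the margin.

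**What the promised analysis would offer.** The ANCOVA residual SD is 0.8 × √(1 − r²): 0.693 at r = 0.5 and 0.571 at r = 0.7. With 48 per arm, SE = 0.141 and 0.117. At a true difference of 0, non-inferiority power Φ(0.4/SE − 1.96) is about 81% and 93%.

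**Precision.** Variance relative to ANCOVA at r = 0.5 / 0.7 / 0.8:
- Change score, 2/(1 + r): 1.33 / 1.18 / 1.11.
- Follow-up value only, 1/(1 − r²): 1.33 / 1.96 / 2.78.

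**The case against.** The SAP does follow the test list in protocol 11.2.4. That section does not name laboratory HbA1c as a non-inferiority endpoint, its non-inferiority clause is conditional, and the stated secondary objectives are descriptive. The synopsis refers to HbA1c data without the word laboratory. On this view the root defect is a conflict inside the protocol, which the SAP settled in one direction. This stands in part: the departure is from the synopsis, and the laboratory reading is an inference, though the only one that fits a secondary HbA1c endpoint. It does not excuse the empty modifications section.

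It can also be said that nobody plans to read non-significance as non-inferiority, that the misreading rate runs from 31% to 0.02% depending on an unknown correlation, and that a significant difference within the margin would be correctly reported as significant. All true. The figures show how far the test and the promised question can diverge; they do not predict an error in this trial. At r near 0.8 the two almost coincide.

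Reusing the primary analysis also needs care. SAP 7.4.1 states the difference as Omnipod minus Medtrum, whereas protocol 11.1 and SAP 5.1 use Medtrum minus Omnipod. Protocol 11.2.4 describes the primary method as an ANOVA on device alone, so the support for ANCOVA comes from the synopsis and SAP 7.4.1. No rule covers missing 3-month laboratory values. These bear on the wording of the fix, not on the need for it. Finally, unadjusted comparisons of the other endpoints are valid; adjusting them is only a gain in precision.

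**Conclusion.** The concern holds. The synopsis promises a non-inferiority analysis, the SAP replaces it with a difference test in ITTm only, and no modification is recorded. The synopsis and protocol 11.2.4 also disagree on the secondary methods. These findings rest on the text alone and are firm.

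The size is conditional on the assumed SD, numbers, margin and correlation. With 48 per arm, a non-significant result can coexist with an upper limit above 0.4 unless r is about 0.80 or higher (0.84 with 40 per arm). The primary analysis and its conclusion do not change. What is lost is the ability to say whether laboratory HbA1c agrees with it. This should be corrected before the analysis.

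**What to change.** Reconcile the synopsis with protocol 11.2.4, then choose one route.

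1. **Restore the analysis.** In SAP 7.4.2, model 3-month laboratory HbA1c by ANCOVA on arm and D0 laboratory HbA1c. Report the Medtrum-minus-Omnipod difference with its 95% CI and judge the upper limit against an explicitly stated margin (0.4 if the primary margin is carried over), in PP and ITT as protocol 11.2.1 requires. Write the sign and the reference level explicitly instead of copying them from SAP 7.4.1, and state how missing 3-month values are handled.
2. **Remove it openly.** Record the removal in SAP section 6 and state that a non-significant test will not be read as non-inferiority.

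Optionally, use baseline-adjusted ANCOVA for time in range, mean glucose and insulin dose. For consistency, show the 3-month laboratory sample in protocol Table 2 and section 7.5. The endpoint definitions already require it, but those two places do not list it.

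The cost is SAP wording, an adapted copy of the primary-model code and an entry in section 6. No data are needed beyond those the endpoint and baseline sections already specify.
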